### **Peer Coach-Veteran Sessions**

**Method of Contact:** Participants will choose whether they want to meet in person or have telephone contacts (or a combination). In IMPPRESS, most chose to have subsequent meetings over the phone for convenience. Prior peer mentoring studies with Veterans have used a mix of in-person and telephone contacts and have had positive results.

**Frequency of Contacts/Meetings:** Peer coaches will be asked to contact/meet with Veterans a minimum of two times per month via telephone or in-person. [name], in her booster sessions and individual calls with coaches, will monitor and help to encourage contacts at this interval.

**Manual:** Veterans will be given a manual identical to Section 1 of the peer coaches' manual (i.e., without the section on being a peer coach). (See Table 1, Column 1)

**Content of Contacts:** As we have learned from our other pain self-management studies and IMPPRESS, the content of each meeting is variable depending on a Veteran's particular needs. However, regardless of specific content (i.e., the specific self-management

strategies discussed), coaches will be asked to 1) review self-management strategies/exercises (based on manual, See Table 1, Column 1), 2) help the Veteran to make adjustments if strategies are not working, 3) help the Veteran to set, follow up on, and be accountable to goals, 4) and motivate and listen to the Veteran. As part of this motivation, coaches will be encouraged to discuss their personal experiences with pain self-management and how they overcame obstacles or handled setbacks and frustrations, and to feel free to engage in conversation that is social in nature if comfortable and appropriate for the situation. Coaches will not advise on medications or medical questions, but will recommend Veterans see their physicians.

Record of Contacts: Peer coaches will be asked to log their sessions with each Veteran, including, date, length, format (phone, in-person), brief notes on content, and any other pertinent information, to allow us to track number and content of contacts. Study staff will maintain regular contact with the peer coaches to ensure logs are being completed, to facilitate collection of logs, and to offer feedback (i.e., if details are missing, or if the peer coach is doing an exceptional job with logs). Logs are simple, straightforward, and typically take less than 5 minutes to complete.

Optimizing Intervention Fidelity: We will employ the following facilitation strategies to optimize fidelity to the intervention: 1) a detailed intervention manual; 2) peer coach training; 3) regular peer coach booster sessions; 4) observer-rated fidelity assessment with feedback to coaches during intervention (which reinforces the importance of protocol adherence and provides constructive feedback to maintain strengths and identify areas for improvement).

### **Data Collection Protocol for Primary and Secondary Measures (Aims 1 and 2)**

Assessments will be given at baseline, 6 and 9 months. Participants (intervention and control) will receive \$30 per assessment. We will administer the same measures to peer coaches and Veterans, because research suggests peer coaches also benefit from peer interventions. Moreover, we want to determine whether the peers experience any negative effects related to their participation.

After obtaining informed consent, a research assistant will administer a baseline assessment to gather socio-demographic data, review the Veteran's history with an emphasis on previous and current pain treatments, and administer measures of primary and secondary outcomes. These assessments will take approximately 30 minutes each.

**Aim 1 (Primary Outcome): To compare 6- and 9-month effects of peer-supported chronic pain self-management versus controls on overall pain.** Overall pain will be measured with the Brief Pain Inventory (BPI) total score. The BPI was developed to assess the severity of pain and the impact of pain on daily functioning, and has been validated in primary care studies. The BPI is the average of two scores: pain intensity and pain interference. The pain intensity score is an average of 4 ratings of 0 (no pain) to 10 (pain as bad as you can imagine) for current, least, worst, and average pain in the past week. The BPI pain interference score averages seven ratings, 0 (does not interfere) to 10 (interferes completely), of interference with general activity, mood, walking ability, normal work, relations with other people, sleep, and enjoyment of life. The BPI total score will be used as the primary outcome measure because BPI total has been shown to be highly responsive to change in clinical trials. The BPI has been shown to have strong internal consistency in its original validation study (Cronbach's  $\alpha = 0.77$ ), the SCAMP study ( $\alpha = .83$ ), and IMPPRESS ( $\alpha = .88$ ); and the BPI assesses the two most important domains—severity and interference—recommended for pain studies.

**Aim 2 (Secondary Outcome Measures): To compare 6- and 9-month effects of peer-supported chronic pain self-management versus controls on self-efficacy, pain coping,**

**patient activation, social support, health-related quality of life, and health service utilization.** We will measure self-efficacy with the Arthritis Self-Efficacy Scale, a 6-item measure that our team has used in prior studies. Patients respond to each item with their degree of certainty on a scale ranging from 1 (very uncertain) to 10 (very certain). In the SCAMP study (with primary care patients, including 40% Veterans, with pain and depression), this scale had high internal consistency (Cronbach's  $\alpha=.88$ ).

Pain coping will be measured with the Pain Catastrophizing Scale, a 13-item scale that assesses catastrophizing—a pain belief that has been found to be a strong predictor of poor treatment response. Validation studies have found strong evidence of criterion-related, concurrent, and discriminant validity. In IMPPRESS this scale had high internal consistency (Cronbach's  $\alpha=.95$ ).

Patient activation will be measured with the Patient Activation Measure (PAM) Short Form, a 13-item scale that assesses patient knowledge, skill, and confidence for self-management of one's chronic health condition. The PAM has been demonstrated reliable and valid in a variety of studies, including IMPPRESS and other work by our team, with reliability ranging from  $\alpha = .87-.88$ .

Social support will be assessed through the Multidimensional Scale of Perceived Social Support. The MSPSS includes 12, 7-point Likert scale items. The test-retest reliability and internal consistency is high, ranging from  $\alpha=.84-.95$  across a variety of studies, including IMPPRESS.

Health-related quality of life will be measured with the RAND SF-36, developed as part of the Medical Outcomes Study.

Health care utilization will be assessed using procedures similar to those we have used in prior studies. Our Data Management group will run CPRS queries for each participant over the 9-month intervention period to identify the following: outpatient visits, ED visits, phone visits, non-opioid and opioid analgesic prescriptions.

### **Other Measures**

- 1) Sociodemographics: age, sex, race, education, marital and job status, income
- 2) Pain Treatment History questionnaire (includes current therapy for pain)

Because depression, anxiety, and pain are common comorbid conditions, we will also administer the following measures:

- 3) Depression: PHQ-8; 4) Anxiety: GAD-7

### **Data Analysis**

**Sample Size Determination.** Our sample size is calculated based on estimated intervention effect on the primary outcome, the Brief Pain Inventory (BPI) total score, a continuous measure. Effect sizes for the BPI in past studies by our team have ranged from .4 to .6. Because this is our first large-scale trial with peer coaches, we will conservatively power the study based on an effect size of .4. To test for a significant difference between the BPI change from baseline to the primary 6-month endpoint between the treatment and control arm, will use a linear mixed model. With a two-sided test and a Type I error of .05, we will have 80% power to detect a .4 effect size with 102 Veterans and 34 peer coaches in the treatment group and 80 Veterans in the control arm, assuming equal variance across the two treatment arms, 3 Veterans per peer coach, and an intra-class correlation (ICC) in the treatment group of .3, which was observed in IMPRESS. (A smaller N is required in the control group because they are not nested within peer coaches.) In our prior chronic pain trials at RVAMC, retention rates were >90%. With a conservative 15% attrition rate, we will need 120 (102/.85) Veterans in the treatment arm, 40

coaches, and 95 (80/.85) Veterans in the control arm, for a total N = 215 Veterans and N = 40 coaches. We plan an intent-to-treat analysis approach.

Consistent with previous studies at RVAMC, the sample will include at least 15% minorities, reflecting the demographics of our medical center. In our SCAMP study, Blacks comprised 16% of the Veteran sample and 13% in ESCAPE. We do not plan to over-sample minorities or power sufficiently to explore racial differences in treatment response. The racial/ethnic composition of RVAMC and participating CBOCs makes exploring racial differences in treatment response impractical unless we employed special efforts to recruit minorities other than Blacks.

**Randomization.** Veterans will be randomly assigned to one of the two study arms using a table of random numbers generated by our statistician, [name]. To obtain the random treatment assignment for the 215 Veterans, five blocks of 43 Veterans will be used, and random treatment allocation will occur within each block to maintain the allocation ratio consistently across blocks. This block size is large enough to prevent investigators and research staff from guessing which treatment comes next in the sequence, while still allowing the allocation ratio to remain consistent.

**Data Analysis: Baseline Comparability.** Because of the size of this study, it is expected that randomization will produce treatment groups that are comparable and balanced. To test this assumption, we will tabulate baseline characteristics of participants and assess for potential imbalance in variables such as sociodemographics, depression, and anxiety across study arms. Additionally, descriptive statistics for baseline characteristics of peer coaches will be assessed (e.g., treatment history, including opioid use). Continuous variables will be assessed with graphical displays and summary statistics (means, standard deviation, range, etc.). Frequency distributions and percentages will be calculated for categorical data.

**Data Analysis for Aim 1.** We will summarize total BPI score at each time point (baseline, 6, and 9 months) for both study arms. To compare the primary outcome of total BPI score at each time point relative to baseline between two treatment arms, we will use a linear mixed-effects model fit to all time points. This model will allow us to compare the change in BPI from baseline to 6 months (primary endpoint) between treatment groups, while accounting for the correlation of measurements from the same Veteran/peer coach and adjusting for confounding factors. Fixed effects in the model will include an indicator for treatment group, time (baseline, 6, and 9 months.), treatment group by time interaction, and covariates found to differ significantly between treatment and control arm. Random effects will include a random patient-specific intercept and a random effect for peer coach within the treatment arm only. Additionally, the variance may be allowed to differ between treatment and control arms. Because this is a randomized trial design we do not expect covariates to significantly differ between the two groups. However, if there are statistically significant differences, these covariates will be included in the model. The linear mixed model for subject  $i$  in therapy group  $j$  at time  $k$  is

$$y_{ijk} = \beta_{10} + b_i + x_{ijk}'\beta + \gamma_{11}t_{ij1} + \gamma_{12}t_{ij2} + (1 - I_{ijk})r_{ijk} + (\beta_{20} + b_i + \gamma_{21}t_{ij1} + \gamma_{22}t_{ij2} + u_j + e_{ijk})I_{ijk}$$

where  $I_{ijk}$  is an indicator if patient is assigned to the treatment group,  $x_{ijk}$  is a vector of fixed covariates,  $t_{ij1}$  is an indicator for the 6-month time point,  $t_{ij2}$  is the indicator for the 9-month time point,  $b_i \sim N(0, \varepsilon^2)$  are patient-specific intercepts,  $\mu_j \sim N(0, \sigma_j^2)$  is the random effect due to peer coach  $j$ ,  $e_{ijk} \sim N(0, \sigma_T^2)$  and  $r_{ijk} \sim N(0, \sigma_C^2)$  are the residual errors for each treatment group. All analyses will include checking of assumptions and model fit. Our statistical model, which accounts for nesting of Veterans within peer coaches, will allow us to calculate the intra-class

correlation (ICC) in the treatment group to evaluate whether there are substantial variations among peer coaches. In secondary analyses, we will also look at the BPI subscales of pain intensity and interference separately, using a similar mixed-model approach and adjusting for multiple comparisons using the Šidák method to maintain the overall confidence at 95% and to adjust for multiple comparisons. To determine if fidelity moderates patient outcomes, we will include the peer coach fidelity score by treatment group interaction and the interaction (fidelity score by time by treatment group) for the 9-month time point in the model above.

**Data Analysis for Aim 2.** Secondary measures of self-efficacy, pain coping, patient activation, social support, and health-related quality of life are continuous measures; thus the linear mixed-effects model described above will also be appropriate to analyze these measures. If a linear mixed model does not seem appropriate for a given scale, then a generalized linear mixed-effects model will be used. Since there will be a number of secondary outcomes, we will use the Šidák method. Health care utilization (number of ED visits, hospitalizations, outpatient visits, telephone visits, and analgesic prescriptions, including opioids) over the 9-month intervention will be analyzed using a generalized linear mixed model, assuming the counts follow a Poisson or negative binomial distribution. Explanatory variables in the model will include treatment indicator and, if necessary, a random effect for peer coach within the treatment group only. Covariates that significantly differ between groups will be included. If counts include a high proportion of zeros, a zero-inflated count model may be required.

**Missing Data.** We conservatively anticipate 10-15% attrition based on our prior studies, which had attrition rates <10%. Attrition is reflected in the sample size calculation. We will compare patient demographic characteristics between those who withdraw and those who do not to verify whether there are characteristics that discriminate dropouts. If the dropout mechanism appears to be Missing At Random, we will simply use all observed outcomes for the analysis. Under circumstances where power loss is of concern, we will use multiple imputation procedures to make use of all relevant observed variables. If data are found to be Missing Not At Random (MNAR), we will use appropriate models (i.e., selection models, pattern mixture models) to account for the missing data mechanism.

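### The stated 80% power for a 0.4 effect does not follow from the listed inputs, which give 57% to 76% when no baseline correlation is credited

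*Combined protocol and SAP*

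**What the plan says.** Under Sample Size Determination in the Data Analysis section, the primary test is of a "significant difference between the BPI change from baseline to the primary 6-month endpoint between the treatment and control arm", using a linear mixed model. For a two-sided test at 0.05 the plan states that "we will have 80% power to detect a .4 effect size with 102 Veterans and 34 peer coaches in the treatment group". The comparison arm is to contribute 80 evaluable controls. On variances the calculation is described as "assuming equal variance across the two treatment arms". Its clustering inputs are "3 Veterans per peer coach, and an intra-class correlation (ICC) in the treatment group of .3". Attrition of 15% is added afterwards, giving 120 and 95 enrolled, so 102 and 80 are evaluable numbers.

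Under Data Analysis for Aim 1, the analysis model is fitted to baseline, 6 and 9 months: "Fixed effects in the model will include an indicator for treatment group, time (baseline, 6, and 9 months.), treatment group by time interaction". On the random part the plan says: "Random effects will include a random patient-specific intercept and a random effect for peer coach within the treatment arm only". In the model equation the coach term carries only a coach index and no time index. The plan says of this model: "This model will allow us to compare the change in BPI from baseline to 6 months (primary endpoint) between treatment groups".

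Neither paragraph gives a baseline-to-6-month correlation, says which SD the 0.4 is measured in, or says whether the ICC of 0.3 is for raw or change scores.

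**The concern.** The power sentence reads as a complete specification, yet the numbers look too small for the result. With 80 controls, 102 independent treated Veterans would already fall short of 80% power for a 0.4 effect, and these 102 are clustered in threes with a sizeable ICC.

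The enrolment target of 215 Veterans and 40 coaches, and the claim that the trial is conservatively powered at 0.4, both rest on this figure. If no baseline correlation was assumed and total variances are equal, the chance of missing a true 0.4 effect at 102 and 80 is about 1 in 3 (ICC applying to change scores) or 1 in 4 (coach effect cancelling), not the 1 in 5 stated. A null primary result could then be over-read as evidence against peer coaching.

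**Working it through.** **Inputs** (all from Sample Size Determination): effect d = 0.4; two-sided 0.05; 102 treated Veterans in 34 coaches of 3; 80 controls; ICC 0.3 in the treated arm; equal variance; stated power 80%.

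**Formula.** Difference of two means with clustering in one arm only, normal approximation, with variances in units of the SD that defines d:

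v = V_T × (1 + 2 × ICC)/102 + V_C/80, and power = Φ(d/√v − 1.96).

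The design effect is 1 + (3 − 1) × 0.3 = 1.6.

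**Attempt to reproduce 80%, with no baseline credit**

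| Reading | v | Power | Effect detectable at 80% |
|---|---|---|---|
| 1. ICC applies to the analysed quantity, equal total variance | 1.6/102 + 1/80 = 0.02819 | 66.4% | 0.470 |
| 2a. Equal residual variance, 0.4 in control-arm SDs | (1.6/0.7)/102 + 1/80 = 0.03491 | 57.2% | 0.523 |
| 2b. Equal residual variance, 0.4 in treated-arm total SDs | 1.6/102 + 0.7/80 = 0.02444 | 72.5% | 0.438 |
| 3. No clustering penalty | 1/102 + 1/80 = 0.02230 | 76.4% | 0.418 |

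For reading 1, √v = 0.16789, 0.4/0.16789 = 2.3825, and Φ(2.3825 − 1.96) = 0.664. For reading 3, √v = 0.14934 and 0.4/0.14934 = 2.678, giving 0.764. Simulation of readings 1 and 3 (40,000 runs each) gave 0.662 and 0.762. A Satterthwaite t test lowers the four figures by about 0.5 to 1 point.

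**Reading 3 and the Aim 1 model.** The coach effect there is constant over time, so it cancels from the baseline-to-6-month change. The generalised least squares variance of the treatment-by-6-month contrast confirms this: it is the same with coach variance 0 or 0.3, and power is 76.4% when 0.4 is in change-score SDs.

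**Ceiling.** For 80% power v must be (0.4/2.8016)² = 0.020385. With 80 controls and 102 treated, the design effect would have to be (0.020385 − 0.0125) × 102 = 0.804, that is an ICC of (0.804 − 1)/2 = −0.098. Equivalently, 80% needs 1/(0.020385 − 0.0125) ≈ 127 independent treated Veterans, or about 1.6 × 127 = 203 clustered ones. Every reading equals reading 3 at ICC 0 and worsens as the ICC rises, so no ICC of zero or more reaches 80%.

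**What would reach 80%.** Let r be the baseline-to-6-month correlation, equal in both arms, with 0.4 in raw-score SDs. Then 80% requires:

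- change contrast, coach effect cancelling, 2(1 − r) × 0.02230 = 0.020385: r ≈ 0.54;
- change contrast, coaches accounting for 0.3 of the change variance, 2(1 − r) × 0.02819 = 0.020385: r ≈ 0.64;
- change contrast, coach variance of 0.3 raw-score units added to the change, (2(1 − r) + 0.6)/102 + 2(1 − r)/80 = 0.020385: r ≈ 0.67;
- baseline-adjusted analysis, (1 − r²) × v = 0.020385: r ≈ 0.53 under reading 1, and 0.29 to 0.65 across the four readings.

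The baseline-adjusted case is not clearly the Aim 1 model, which fits baseline as an outcome with a treatment-by-time interaction.

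Power for the change contrast, 0.4 in raw-score SDs:

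| r | 0.3 | 0.4 | 0.5 | 0.6 | 0.7 |
|---|---|---|---|---|---|
| Coach effect cancels | 62% | 69% | 76% | 85% | 93% |
| Coaches account for 0.3 of change variance | 52% | 59% | 66% | 76% | 87% |

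The credit is therefore not automatic. Below r = 0.5 the change contrast does worse than readings 1 and 3.

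**Better retention.** With about 10% loss (108 and 85), readings 1 and 3 give 69 to 70% and 79%. With no loss (120 and 95) they give 74% and 83%.

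**The case against.** The strongest reply is that leaving out baseline credit is the check's condition, not the plan's. The named test is a mixed model for change with a patient intercept, so a within-patient correlation belongs to it. A correlation of about 0.54 restores 80% when the coach effect cancels and 0.4 is in raw-score SDs, and nothing in the documents makes that value implausible. The plan also cites a published source of sample size formulae, which may define the ICC, the variance assumption and the effect size. That source could not be consulted. On this view the fault is an unreported input, not an arithmetic slip.

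Much of this stands, and it limits the conclusion: true power is not shown to be 66%. The 57% to 76% range is also not a floor. With 0.4 in raw-score SDs and a low correlation, power falls below it. But a model that can use a correlation does not supply its value, and a citation does not either. The plan lists its other design inputs in detail and omits the one that would have to carry the result.

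It can also be said that the gap may be small in practice, because the plan reports retention above 90% in earlier trials. On the cancelling reading that is fair (79% at 108 and 85). On reading 1 a gap of about 10 points remains. In any case the plan attaches its 80% to 102 and 80.

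**Conclusion.** The concern holds. At 102 and 80, two-sided 0.05 and an effect of 0.4, the stated inputs give 66% on the most direct reading, 57% or 73% under equal residual variance, and at most 76%. None reproduces 80%. These figures assume no baseline credit and the normal approximation.

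Reaching 80% needs something the plan does not state: 0.4 in raw-score SDs together with a correlation of about 0.54 (coach effect cancels) or 0.64 to 0.67 (coaches affect change, equal total variance), or a baseline-adjusted analysis with its own correlation. The sample size paragraph and the Aim 1 model also need reconciling. The first lists an ICC of 0.3 as an input and explains the smaller control arm by the absence of nesting, while in the second the coach effect drops out of the primary contrast.

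Confidence is high that the figure does not follow from its inputs. What the true power is cannot be settled from the documents.

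**What to change.** Replace the power sentence under Sample Size Determination, in one of two ways.

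- **If no baseline correlation was assumed**, state: With 102 Veterans nested in 34 peer coaches (3 each), 80 controls and a two-sided 0.05 test, with the effect size in SDs of the 6-month change score and equal total variance in the two arms, power for a 0.4 effect is about 66% if the ICC of 0.3 applies to change scores (80% at about 0.47), and about 76% if the coach effect is constant over time and cancels from the change (80% at about 0.42).
- **If a baseline correlation was assumed**, state its value, the SD to which 0.4 refers, whether the ICC of 0.3 is for raw or change scores, and the formula used. Then report the power recomputed under the Aim 1 model.

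The change-score SD in the first option is itself an assumption, so the sponsor should adopt that wording only if it is what was meant.

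The cost is wording in the protocol and SAP. Enrolment, visits and data collection do not change. The one drawback is a less favourable stated figure if no correlation was assumed.

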### **Recruitment and Training of Peer Coaches**

Recruitment: We have three primary sources for recruiting peer coaches: 1) Veterans who served as peer coaches in IMPPRESS (7 out of 9 expressed interest in serving as a coach again); 2) Veterans who completed the intervention arm of one of our previous chronic pain studies involving pain self-management instruction (ESCAPE, PI: [name]; CAMEO, PI: [name]; SCOPE, PI: [name]). In these studies completers were asked for permission to be contacted for future studies. We successfully recruited 10 peer coaches for IMPPRESS in one month using this approach. From these two completed and one ongoing study we have a pool of approximately 250 potential peer coaches. 3) Veterans with chronic pain (see ICD-9 codes in Section D2c) who are recommended by their PCPs. Although we did not need this strategy in IMPPRESS because of successful recruitment of participants from prior studies, one of our co-investigators, [name], has successfully used this method for peer studies of Veterans with diabetes.

Manual: Each peer coach will be given a manual to refer to and serve as a guide during the intervention. The Peer Coach Manual consists of two parts: 1) Self-Management Knowledge (this portion is identical to the Veteran manual), and 2) How to be a Peer Coach. See Table 1. This manual was developed and refined in IMPPRESS, drawing on the study manual from [name] ESCAPE trial (Part 1), and on the Peer Specialist Manual used by VHA's Office of Mental Health Services (Part 2, shared by [name], Director of VA Peer Support Services, see letter of support). In addition, during IMPPRESS, our study psychologist, [name], developed a section on motivational strategies, grounded in the motivational interviewing literature. The peer coach manual is in Appendix 1.

Training: Three to 4 coach training sessions will be scheduled as coaches are recruited. Once 10 coaches are recruited, a training session will be scheduled, and coaches will be assigned Veterans. This process will continue until all peer coaches are recruited, trained, and matched with Veterans.

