**Inclusion/Exclusion Criteria:** Once potentially eligible Veterans are identified and PCPs have granted permission to recruit, we will contact Veterans to identify those who meet study inclusion/exclusion criteria. Potential participants will be told that we are conducting a study to learn how Veterans can help other Veterans with chronic pain management, and that they will be randomly assigned either to the Veteran peer coach group or to the group receiving a pain self-management class. Eligible patients must 1) have musculoskeletal pain in the low back, cervical spine, or extremities (hip, knee, or shoulder) for  $\geq 3$  months; 2) have at least moderate pain severity, defined by pain  $\geq 5$  on a 0 (no pain) to 10 (worst pain imaginable) scale; and 3) indicate willingness to engage in phone or in-person contact on a regular basis with another Veteran. We have identified approximately 26,000 unique outpatients who meet criteria 1 and 2. Patients will be excluded if the electronic medical record indicates a diagnosis of a psychotic disorder (e.g., ICD-9 codes 295-295.9 for schizophrenia), current substance dependence (e.g., ICD-9 codes 304-304.9), severe medical conditions precluding participation (e.g., NY Heart Association Class III or IV heart failure, ICD-9 codes 428-428.9), or if the eligibility screener given to prospective participants reveals active suicidal ideation, severe hearing or speech impairment, or pending surgery for a musculoskeletal condition (e.g., back surgery).

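### Fixed blocks of 43 at 24:19 do not prevent guessing: about 10 of 215 assignments become certain to anyone who keeps count, and the plan names no other concealment step

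*Combined protocol and SAP*

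**What the plan says.** The Randomization paragraph of Data Analysis has the statistician generate a table of random numbers and then fixes the structure: "five blocks of 43 Veterans will be used, and random treatment allocation will occur within each block to maintain the allocation ratio consistently across blocks". It defends the block length on two grounds. The first is concealment: "This block size is large enough to prevent investigators and research staff from guessing which treatment comes next in the sequence". The second is balance: "while still allowing the allocation ratio to remain consistent".

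The arm sizes come from Sample Size Determination: 120 Veterans in the treatment arm, and "95 (80/.85) Veterans in the control arm, for a total N = 215 Veterans". The split within a block is not printed.

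Three other places bear on whether assignments are visible:

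- Recruitment and Training of Peer Coaches, Training: "Once 10 coaches are recruited, a training session will be scheduled, and coaches will be assigned Veterans".
- Control Arm: controls attend a class led by a member of the study team and have their baseline assessment immediately beforehand.
- Recruitment of Veterans, Inclusion/Exclusion Criteria: "we will contact Veterans to identify those who meet study inclusion/exclusion criteria".

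The text available for review does not say who holds the list, how an assignment is released, or that release follows consent and eligibility. It describes no masking of staff and no stratification by clinic.

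**The concern.** Within a fixed block of known composition, each assignment made narrows what is left. Once one arm's places are used up, every remaining assignment in that block is determined. A longer block postpones that moment and makes it rarer, but cannot abolish it, and here it recurs five times. Block length is also the only safeguard the paragraph offers.

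The arms cannot be disguised, since one receives a coach and the other a class. One unstratified sequence appears to serve all nine clinics. A study team could therefore plausibly know both running counts. If the next arm is known, entering a particular Veteran sooner or later can depend on that arm. The primary outcome is the self-reported BPI, so selection on likely response would feed into the treatment contrast.

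**Working it through.** **Inputs.** 102 and 80 evaluable Veterans, 15% attrition, 3 Veterans per coach, ICC .3 and 40 coaches (Sample Size Determination); five blocks of 43 at a constant ratio (Randomization).

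**Step 1: reproduce the plan's figures.** 102/.85 = 120. 80/.85 = 94.1, rounded up to 95. The total is 215 = 5 × 43.

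**Step 2: block composition.** 120/5 = 24 and 95/5 = 19. Both are whole numbers, so a constant ratio means 24:19 in every block. Because 24:19 is in lowest terms, 43 is the shortest block that keeps the exact ratio.

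**Step 3: certain assignments.** For a random ordering of T coaching and C class places, the expected run of identical assignments at the end of the block is

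T/(C+1) + C/(T+1) = 24/20 + 19/25 = 1.20 + 0.76 = 1.96.

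Over five blocks this is 9.8 of 215, or 4.6%. The last assignment of each block is always certain, so the minimum is 5. The last two or more are certain in 49.5% of blocks, the last three or more in 24.3%, and the last four or more in 11.8%. A simulation of 50,000 blocks also gave a mean of 1.96.

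**Step 4: near-certain assignments and overall guessing.** With t and c places left, the chance that the next assignment is coaching is t/(t+c). Exact recursion over all paths through a 24:19 block gives:

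| Quantity | Per block | Over 215 |
|---|---|---|
| Certain | 1.96 | 9.8 (4.6%) |
| Predictable at 75% or more | 4.0 | 20.0 (9.3%) |
| Predictable at two-thirds or more | 8.2 | 41.0 (19%) |
| Correct, always guessing the arm with more places left | 26.0 | 129.9 (60.4%) |
| Correct, always guessing coaching | 24 | 120 (55.8%) |

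The gain over the naive guess is 60.4 − 55.8 = 4.6 percentage points.

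**Step 5: what varied lengths achieve.** Take lengths drawn at random from 27, 36, 45, 54 and 63 at 5:4. Expected arms are 215 × 5/9 = 119.4 and 215 × 4/9 = 95.6, about 119:96. Both schemes were simulated with the same rule: guess class when coaching is more than 0.5 ahead of its ratio, otherwise guess coaching. Correct guesses were 59.8% with fixed 43 and 59.1% with varied lengths. A guesser who knows the set of possible lengths gets about 59.3%. Certain assignments fall from 9.8 to about 0.6.

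**Step 6: cost in arm sizes.** Coach capacity is 40 × 3 = 120. Under varied lengths about 19% of simulated trials put more than 120 Veterans in coaching, usually by 1 to 3. For power, the design effect in the coached arm is 1 + (3 − 1) × .3 = 1.6, and information is 1/(1.6/n_T + 1/n_C). Taking the plan's 80% at 120:95 as reference, a shift of 7 Veterans either way (127:88 or 113:102) gives 79.8%.

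**The case against.** The strongest reply is that the sentence is nearly right in practice. About 95% of assignments are never certain, and a perfect counter gains only 4.6 points over always naming the larger arm. The 24:19 split has to be derived. Exploiting it needs a complete ordered tally across nine clinics, and nothing in the documents says that anyone keeps one. All of this stands. It limits the size of the point, but it does not rescue a claim that guessing is prevented.

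Four stronger readings are tempting, and the documents do not support them.

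- **That the trial is declared open and staff are known to count both arms.** Neither is stated. Both are inferred from coach assignment, from the control baseline being held just before the class, and from the single sequence.
- **That the eligibility criteria give staff room to steer entry.** They show little discretion. Severe medical conditions are taken from diagnoses in the medical record, willingness is indicated by the Veteran, and pain has a numeric threshold of 5. The timing of entry could be influenced, but the documents do not say who controls it.
- **That the analysis leaves any such selection wholly uncorrected.** Data Analysis for Aim 1 compares change from baseline and adds covariates that differ significantly, which deals at least partly with selection on baseline BPI. Selection on unmeasured prospects for change would remain.
- **That varied blocks make the sequence much harder to guess overall.** Under the same rule the drop is 59.8% to 59.1%.

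It is also fair to say that keeping blocks of 43 and withholding their size and composition would capture much of the benefit.

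**Conclusion.** The concern holds in a limited form. Blocks of 43 at 24:19 reduce guessing but do not prevent it: 9.8 of 215 assignments are certain on average, never fewer than 5, and about 20 are predictable at 75% or more. These figures are exact if the observer knows the block length and composition and has an ordered tally of both arms. That last condition is plausible but inferred.

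A reader might go on to conclude that the BPI contrast will be biased by a definite amount. The documents give no basis for that: they say nothing about staff acting on predictions, or about how far prognosis would differ if they did. For scale only, assume every certain assignment is exploited in opposite directions in the two arms, with a prognosis shift of .25 to .5 SD. Of the 9.8, 6.0 are coaching (5 × 1.20) and 3.8 are class (5 × 0.76). At .5 SD the contrast moves by (6.0/120) × .5 + (3.8/95) × .5 = .045 SD; at .25 SD, by .0225 SD. That is 6% to 11% of the planned .4 effect under a deliberately unfavourable assumption.

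This is a correctable weakness in concealment, not a threat to the trial. It merits a change because the plan relies on a property the scheme lacks and the correction is nearly free.

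**What to change.** In the Randomization paragraph of Data Analysis:

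1. Replace the five blocks of 43 with permuted blocks of randomly varied, moderately large length, for example 27 to 63 in steps of 9 at 5:4. Do not use a set of short blocks such as 9, 18 and 27, which simulation shows is easier to guess from running counts (about 62% to 63% correct).
2. Keep the actual lengths out of the protocol and away from recruiting staff, in a document held by the statistician.
3. State that the statistician holds the list and releases one assignment at a time, only after consent and confirmed eligibility.
4. Delete the sentence on guessing, or say that the scheme reduces predictability.

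The cost is a short wording change and a regenerated list, with no extra recruitment. The split may differ from 120:95 by a few Veterans, with negligible loss of power. In about 19% of trials coaching would exceed the capacity of 120, so the plan should either allow for a few extra coach matches or stop coaching assignments at 120. The second option makes any assignments after the cap predictable, so the cap should also be withheld from recruiting staff.

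If the sponsor prefers to keep blocks of 43, items 3 and 4 still apply, and block size and composition should be withheld from recruiting staff.
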